7.10.3.4 Other Exploratory Analyses

Relationships of sensitivity and specificity may be evaluated post-hoc with respect to additional covariates including, but not limited to, tumor size, tumor type, and tumor location.

7.11 Safety Endpoint Analyses

All the analyses in this section will be performed on the Safety population by Part and overall. Patients will be analyzed according to the actual treatment they received.

Repeated or unscheduled results will not be included in the summary statistics but will be included in the individual data listings.

7.11.1 Adverse Events

All adverse events (AEs) will be coded using the Medical Dictionary for Regulatory Activities (MedDRA). A TEAE is defined as an AE that occurs (or worsens) during or after study drug administration and through Day 21 after administration of study drug.

An overview of all AEs will be provided that will include:

- Number of AEs, TEAEs, non-serious TEAEs, and Serious Adverse Events (SAEs)
- Number of TEAEs and SAEs related to study drug
- Number of TEAEs related to study drug with CTCAE grade ≥ 3
- Number of AEs and study drug related SAEs resulting in:
 - Death
 - Subject discontinuation
 - Study drug discontinuation

TEAEs, treatment-related TEAEs, TEAEs by CTCAE grade, TEAEs that lead to discontinuation of study drug, SAEs, and SAEs that lead to discontinuation of study drug, will be summarized by system organ class (SOC) and preferred term (PT).

Infusion related reactions (IRR) will be summarized by PT, and a descriptive summary of the duration of IRR will be provided.

A listing of all AEs, including a separate listing for IRR, will also be generated.

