## 3. STUDY PLAN

### 3.1 Overall Design

This Phase 2 study will be an interventional, open-label, single arm trial where each patient is his/her own “intrapatient” control. All patients will receive a single mg/kg dose of pgsitacianine prior to standard of care surgery.

Patients will have a biopsy confirmed diagnosis, or a high clinical suspicion of a lung malignancy based on MRI, CT and/or PET imaging. A total of up to 40 patients will be enrolled in this trial. Enrollment will be open first to Part 1 with the opportunity to open Part 2 for enrollment following the demonstration of satisfactory pgsitacianine sensitivity and specificity values of 70% or greater in Part 1. The sponsor reserves the right to perform an interim analysis following early enrollment (i.e.,  $n \leq 10$  patients) to determine the feasibility and benefit of pgsitacianine as an adjunct to standard of care surgical resection of lung malignancies. Interim analysis will assess the utility of pgsitacianine based on mean fluorescence intensity analysis, calculation of tumor to background ratios, calculation of sensitivity and specificity, safety, and investigator feedback.

The surgeon will begin by attempting to perform their SOC tumor resection. If the tumor is unable to be located under standard white light conditions, an appropriate FDA-cleared near-infrared imaging device (Examples found in [Appendix 2: FDA-Cleared NIR Imaging Devices](#)) may be used to aid in the location of the primary tumor. Localization of the primary tumor, when unable to be located using white light imaging, in conjunction with pathology confirmed presence of disease will be considered a clinically significant event.

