#### 4.3 Study Drug Safety

The most common and anticipated adverse events related to pgsitacianine include infusion related reactions. These reactions occur in about 1 in 3 patients and tend to be mild or moderate in severity. In general, these reactions initiate within 5 minutes of infusion start and resolve within minutes after onset.

Over the doses evaluated in the Phase 1 ON-1001 study (0.1-1.2 mg/kg), pgsitacianine was well tolerated in patients with solid tumors (HNSCC, BC, CRC, or EC) and showed no dose-limiting toxicity (DLT) (hence the maximum tolerated dose was not reached during the study) or study-drug-related serious adverse events (SAEs). Since no pgsitacianine-related SAEs were reported in Phase 1a, the highest dose from Phase 1a [REDACTED] was selected for further evaluation of safety, PK, and imaging feasibility of pgsitacianine in Phase 1b in 15 additional patients across 4 tumor types (BC, HNSCC, CRC, EC) at administration [REDACTED] before surgery (and imaging).

In Phase 1a and 1b, all 30 patients (100%) experienced treatment-emergent adverse events (TEAEs). The most common TEAEs (ie, reported  $\geq 4$  patients overall) were procedural pain (21/30 patients, 70%), nausea (6/30 patients, 20%), wound complication (4/30 patients, 13%), and constipation (4/30 patients, 13%). The TEAEs of procedural pain and wound complication could be attributed to the surgical procedures (standard of care). Severe (Grade  $\geq 3$ ) TEAEs, none related to study drug, occurred in 6 (20%) patients. Overall, 3 patients experienced 4 TEAEs (dizziness, headache, pain in jaw, and flushing) considered possibly related to the study drug. All TEAEs considered related to study drug were mild (Grade 1) and experienced by patients in the [REDACTED] dose cohort. These TEAEs were consistent with typical complications known to occur following surgery, of which the Investigator could not completely rule out the possible contribution of pgsitacianine.

Transient increases in alanine aminotransferase (ALT) (up to 7 $\times$  upper limit of normal [ULN]), aspartate aminotransferase (AST) (up to 10 $\times$ ULN), and/or alkaline phosphatase (up to 3 $\times$ ULN) levels were reported in 4 patients at  $\geq 1$  time point after dosing; none of these abnormalities were considered to be related to the study drug; These elevations were judged by the Investigator to be complications due to the length of surgery and the duration of anesthesia.

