### **6.3 Surgery and Follow-up Visits**

#### ***Procedures at the time of surgery***

The following procedures will be performed on the day of surgery (before administration of anesthesia and before surgery):

- Record the patient's vital signs
- Obtain blood for routine laboratory tests
- Record all medications being taking, including prescription, over-the-counter, and herbal medications
- Discuss with the patient any new or unexpected changes they are feeling.
- Record any AEs.

Once the patient is under anesthesia, some procedures will occur that would not normally be part of surgery if the patient were not in this study. The SOC surgical procedures will be allowed to continue with the addition of the imaging steps listed below.

- If the primary tumor is not visually apparent using standard approaches, the NIR camera may be used to help locate and guide the resection of the primary tumor.
  - The primary tumor should be imaged prior to excision and following excision on a piece of normal tissue from a distance equal to the operating distance of the camera.
- If the primary tumor is apparent under standard conditions, it will be imaged prior to resection. Additionally, the resected tissue will be imaged using the

intraoperative camera on a section of normal tissue at a distance equal to the operating distance of the camera

- Following the primary tumor resection, margins (both on the excised primary and the affected lung) will be examined using NIR in an effort to detect residual disease
- All SOC lymph nodes to be collected during the operative procedure will be imaged prior to and following excision in a manner identical to the procedures used for imaging the primary resection
- Once the SOC primary tumor resection is complete, the surgeon will examine the thoracic cavity with the intraoperative NIR camera in search of additional fluorescent disease, or lymph nodes that were missed during SOC
- Additional fluorescent lesions, or lymph nodes will be imaged prior to excision, removed and imaged on a section of normal tissue in a manner analogous to the SOC specimens.
- For all resected specimens (including SOC primary tumor, margins, SOC lymph nodes and additional missed disease), fluorescence status and specimen name will be called out by the surgeon for documentation by the clinical research coordinator in the provided Imaging Workbook

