### **9.1 Sample Size**

The sample size for this study will be 40 subjects. This sample size is based on historical experience with similar pilot studies with the goal of informing power calculations for future studies. This study is not formally powered for hypothesis testing. A sample size of 40 subjects will be sufficient for developing further understanding of the endpoints described herein. Sample size calculations account for non-evaluable and drop-out patients.

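### The AE tables pool events from dosing through Day 21 with no split at surgery, so outside the infusion-reaction summary only the open-label relatedness call separates drug events from surgical ones

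*SAP*

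**What the plan says.** Protocol 3.1 describes an "interventional, open-label, single arm trial where each patient is his/her own" control, with one dose given "prior to standard of care surgery". Safety and toxicity are a key secondary objective (Protocol 2.2; SAP Table 1).

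SAP 7.11.1 defines a TEAE as an AE that starts or worsens from dosing through Day 21. It then summarises "TEAEs, treatment-related TEAEs, TEAEs by CTCAE grade, TEAEs that lead to discontinuation of study drug", together with SAEs, by system organ class and preferred term. Neither this section nor Protocol 9.7 divides the period at surgery.

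The plan does provide some separation:
- SAP 7.11.1 summarises infusion reactions by preferred term and duration, with their own listing. SAP 7.9.4 counts patients with infusion reactions and with dose interruptions.
- SAP 7.11.1 includes treatment-related TEAEs, related SAEs and related events of grade 3 or higher. Relatedness is the investigator's call on the five-level scale of Protocol 8.3.
- SAP 7.11.2 and 7.11.3 show laboratory values and vital signs by time point, with change from a pre-dose baseline (SAP 7.3).

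The data for a split at surgery are largely in the schedule. AEs are recorded after dosing (Protocol 6.2) and again under the Protocol 6.3 list headed "The following procedures will be performed on the day of surgery (before administration of anesthesia and before surgery"). Protocol 8.2 collects the time of onset.

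**The concern.** The own-control feature serves the imaging comparison. It gives no safety contrast, because no patient has the operation without the drug. In a pooled AE row, surgical morbidity and drug effects therefore add together.

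The protocol's account of ON-1001 (Protocol 4.3) shows the result. Of the most frequent events it says: "The TEAEs of procedural pain and wound complication could be attributed to the surgical procedures (standard of care"). It puts liver-enzyme rises down to the length of surgery and anesthesia. The four events judged possibly related, in three patients, are described as resembling ordinary post-surgical complications in which a drug contribution could not be fully excluded. The relatedness call is thus least certain where it is most needed.

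Nausea illustrates the gap. Protocol 4.3 lists it among the infusion-reaction symptoms of unoperated volunteers in ON-1004, and as a TEAE in 6 of 30 surgical patients in ON-1001. The SAP gives no onset window or term list for an infusion reaction. Pre-surgical nausea that is not labelled as one goes into the same row as postoperative nausea. At stake is a surgery-free AE incidence that does not depend on an unblinded causality judgment.

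**Working it through.** **The plan's own figure.** N = 40 cannot be reproduced: Protocol 9.1 gives no rate, precision target or error level and says "This study is not formally powered for hypothesis testing". The point does not depend on it; 40 is used below as the denominator.

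**Inputs (Protocol 4.3), with exact (Clopper-Pearson) 95% CIs**

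| Quantity | Count | % (95% CI) |
|---|---|---|
| ON-1001, any TEAE | 30/30 | 100 (88.4 to 100) |
| ON-1001, procedural pain | 21/30 | 70.0 (50.6 to 85.3) |
| ON-1001, nausea | 6/30 | 20.0 (7.7 to 38.6) |
| ON-1001, grade 3 or higher, none related | 6/30 | 20.0 (7.7 to 38.6) |
| ON-1001, patients with a possibly related TEAE | 3/30 | 10.0 (2.1 to 26.5) |
| ON-1004 (no surgery), infusion reaction | 5/17 | 29.4 (10.3 to 56.0) |

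The percentages that the protocol prints agree with its counts.

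**Step 1: what the pooled any-TEAE row can show.** If all 40 patients have a TEAE, the lower limit is 0.025^(1/40) = 91.2%, so the row reads 100% (91.2 to 100) with or without a drug effect.

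**Step 2: how far a drug effect would move that row.** Let s be the proportion with a surgical TEAE and d the proportion with a drug-caused TEAE, assumed independent. The pooled rate is 1 − (1 − s)(1 − d), so the drug adds (1 − s)d. The documents give no s for lung resection; the range is an assumption.

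| s | added if d = 1/3 | added if d = 0.10 |
|---|---|---|
| 0.70 | 10.0 points | 3.0 points |
| 0.80 | 6.7 | 2.0 |
| 0.90 | 3.3 | 1.0 |
| 0.95 | 1.7 | 0.5 |
| 1.00 | 0 | 0 |

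The value d = 1/3 is the protocol's approximate infusion-reaction rate, used only as a drug effect of known size.

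**Step 3: what a pre-surgical period could show with N = 40.** No events of a given type would bound its rate at 1 − 0.025^(1/40) = 8.8%. An event with a true rate of 5% would be seen at least once with probability 1 − 0.95^40 = 87%. One event would give 2.5% (0.1 to 13.2) and four would give 10.0% (2.8 to 23.7). These are coarse figures, but no surgical events enter them.

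**Step 4: end of the AE window.** SAP 7.11.1 stops at Day 21. Protocol Section 8 monitors through Day 28. The schedule footnote runs to the Day 21 ± 10 visit, which is Day 11 to Day 31. The three do not agree.

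**The case against.** The strongest reply is that the main known drug effect before surgery is already reported separately. At about 1 in 3, 40 × 1/3 gives about 13 patients, or 32.5% (18.6 to 49.1), and these are the infusion reactions that SAP 7.9.4 and 7.11.1 summarise. That is right, so the 13 cannot be counted as a gain from the split. A reader might infer that the pre-surgical interval is never tabulated, or that all the safety tables mix drug and surgery. The documents do not support either reading, given the infusion-reaction summary and the laboratory and vital-sign displays by time point.

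The related-TEAE tables also separate: in ON-1001, 30 of 30 patients had a TEAE but only 3 had one judged possibly related. Preferred terms keep procedural pain apart from flushing. This limits the problem to terms that drug and surgery share, and to reliance on open-label judgment.

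A reader might also want the pre-surgical period made the main display of drug toxicity. The documents do not support that. Delayed effects would fall after surgery, and harm from fluorescence-guided resection can arise only then. Nor is the earlier period free of everything but the study drug: diphenhydramine is recommended beforehand, and the dose-to-surgery interval is blacked out in the public text.

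Two practical objections stand in part. Anesthesia start time is not listed as collected, and Protocol 8.1 speaks of onset date where 8.2 speaks of time of onset. The table shells are in a separate document not available here. A split may be planned there, but the SAP text does not call for one.

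**Conclusion.** The point holds as a limited reporting gap. The pooled TEAE, grade and SAE rows cannot separate drug from surgical events, except through the open-label relatedness call and the infusion-reaction summary. Pre-surgical events not classed as infusion reactions have no surgery-free tabulation, which is out of step with how laboratory values and vital signs are handled.

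For the any-TEAE row, a drug effect in one third of patients adds between 10.0 points (s = 0.70) and 0 (s = 1.00). This rests on independence and on an assumed surgical rate. The 30/30 comes from other tumour types and operations, whereas SAP 3.1 notes that only the minimally invasive Part 1 enrolled. The 1-in-3 rate makes no allowance for the recommended premedication. How many events other than infusion reactions the split would show cannot be estimated from the documents.

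It would go too far to infer that the safety objective is answered mainly by surgical morbidity. The study is a descriptive pilot, all AEs are listed, and the primary endpoint, diagnostic measures and sample size are untouched.

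**What to change.** In SAP 7.11.1, add a supplementary display of TEAEs by system organ class, preferred term and grade in two onset periods: before, and from, the start of anesthesia. If that time is not recorded, cut at the day-of-surgery pre-anesthesia AE review or at the start of surgery, and state which. Confirm that the AE form captures the time of onset as well as the date, at least for the day of surgery.

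Keep the pooled total and the infusion-reaction summary. Label the first period as free of surgical events but not of premedication. Label the second as confounded with surgery but able to contain delayed drug effects and harm from fluorescence-guided resection. Name neither as the primary display.

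The cost is one derived variable and one more column per table, with small counts in the first period. No new visit or patient is needed.

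Separately, reconcile the end of the AE window across SAP 7.11.1, Protocol Section 8 and the schedule-of-events footnote.

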Trial Design	This Phase 2 study will be an interventional, open-label, single arm trial where each patient is his/her own “intrapatient” control. All patients will receive a single mg/kg dose of pegsitacianine prior to standard of care (SOC) surgery. It is recommended by the sponsor to administer prophylactic diphenhydramine before administration of pegsitacianine to decrease the possibility of an infusion-related reaction. The study will be conducted in two Parts. Part 1 will enroll patients undergoing minimally invasive procedures (i.e., video-assisted thorascopic surgery [VATS] or robotic surgery). Part 2 will be opened at the discretion of the Sponsor and include patients undergoing open thoracotomy for the removal of their disease. Enrollment will be open first to Part 1 with the opportunity to open Part 2 for enrollment following the demonstration of

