## 4. STUDY DRUG DOSAGE AND ADMINISTRATION

On Day 0 of the study, the patient will receive a [REDACTED] mg/kg dose of pegsitacianine

The volume of drug and total time of infusion will vary by patient and be reliant on the overall required dose. It is the sponsor's recommendation that the clinical site prophylactically dose the subject with diphenhydramine to reduce the likelihood of the subject experiencing an infusion-related reaction.

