There were a total of eight Grade 3 TEAEs, all but one instance (high blood pressure, probably related) were not related to the administration of the study drug.

None of the patients enrolled in the ongoing Phase 2 study withdrew from the study due to a TEAE, or had an abnormal ECG that was considered clinically meaningful and related to the study drug.

In the completed Phase 1 healthy volunteer study to evaluate the pharmacokinetics of pegasitacianine, 5 patients of the 17 dosed (29.4%) experienced an infusion related reaction to pegasitacianine. Patients exhibited symptoms that included diaphoresis, lightheadedness, nausea, warmth/flushing, chest heaviness, palpitations, and back pain/spasms. All TEAEs presented shortly after infusion start (3-5 min) and resolved on their own shortly thereafter (3-5 min duration). One subject chose to discontinue the product and withdrew consent. In the remaining patients, the product was halted and restarted in 2 patients with no re-emergence of symptoms while the remaining 3 patients received the complete dose without pause. All TEAEs were deemed to be mild in severity by the investigator.

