7.9.4 Administration and Exposure of Study Drug

Administration of study drug (planned dose level, total dose administered, total volume administered, infusion flow rate, infusion duration, subjects with infusion reactions, and subjects with dose interruptions) will be summarized using descriptive statistics. Infusion flow rate will be calculated as total volume administered ÷ infusion duration. A listing will also be generated.

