7.11.3 Vital Signs

Vital signs data will be summarized by time point, Part, and change from baseline. A listing will also be provided.

Repeated or unscheduled results will not be included in the summary statistics but will be included in the individual data listings.

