9. APPENDIX 1: SCHEDULE OF EVENTS

	Screening	Dosing		Treatment		
	Days -30 to -1	Day 0 Pre-Dose	Day 0 Post-Dose	Surgery █ - █	Day of Discharge	Day 21 (± 10 Days)
Evaluation						
Informed consent & subject enrollment	X					
Inclusion/exclusion criteria	X	X				
Pregnancy test ^a	X	X				X
Demographic data	X					
Medical history	X					
Physical examination	X				X	X
Karnofsky Performance Status	X					
Height ^b	X					
Body weight ^b	X	X				
Vital signs ^c	X	X	X ^d	X	X	X
12-lead electrocardiogram		X				X
Concomitant medications	X	X	X	X	X	X
Study drug administration			X ^e			
Adverse events review ^f			X	X	X	X

Serum chemistry	X	X		X	X	X
Hematology ^g	X	X		X	X	X
Surgery				X		
Intraoperative Imaging				X		
Pathology evaluation of surgical specimens				X ^h		

Footnotes

- ^a For female subjects, a serum sample or urine dipstick for a pregnancy test will be collected at screening and on Day 0 and Day 21.
- ^b Body mass index will be calculated at Screening only.
- ^c Vital sign measurements will include systolic and diastolic blood pressure, pulse, respiratory rate, and temperature (in degrees Celsius). Blood pressure and pulse will be measured after a resting period of at least 5 minutes in the supine position.
- ^d Patient's vital signs are to be recorded immediately after the infusion and 30 minutes afterward
- ^e The Sponsor recommends the use of prophylactic diphenhydramine prior to study drug administration, in an effort to reduce the prevalence of infusion-related reactions.
- ^f Patients will be assessed for AEs occurring from the time of dosing through Day 21 (± 10 days)
- ^g Hematology assessments may include hemoglobin, hematocrit, erythrocyte count (red blood cells), differential leukocytes, platelet count, and total leukocytes (white blood cells).
- ^h Pathologic analysis of surgical specimens will take place from the conclusion of surgery and up to 10 days after

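### Infusion reactions are reported pooled although diphenhydramine is optional, a Day 0 premedication dose falls outside both medication categories, and unscheduled vital signs reach only the listings

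*SAP*

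**What the plan says.** **Premedication.** Protocol section 4 states: "It is the sponsor's recommendation that the clinical site prophylactically dose the subject with diphenhydramine". The schedule of events in SAP Appendix 1 gives the purpose: "The Sponsor recommends the use of prophylactic diphenhydramine prior to study drug administration, in an effort to reduce the prevalence of infusion-related reactions". Nothing legible makes it mandatory.

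**Expected rate.** Protocol 4.3 names infusion-related reactions as the most common anticipated drug-related event, at about one patient in three. It reports 5 reactions among 17 dosed (29.4%) in the healthy-volunteer study.

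**Reaction reporting.** SAP 7.11.1 states "Infusion related reactions (IRR) will be summarized by PT, and a descriptive summary of the duration of IRR will be provided" and adds "A listing of all AEs, including a separate listing for IRR, will also be generated". Safety analyses are by Part and overall, but SAP 3.1 notes that Part 2 was not opened, so this is one group. SAP 7.9.4 also counts subjects who react and subjects whose dose is interrupted. No display is by premedication, and SAP 7.6 plans nothing by center.

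**Medication categories.** Under SAP 7.9.3 a medication is concomitant if its end date falls after the dosing date or is missing, and prior if its end date falls before it.

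**Vital signs.** Post-dose readings are scheduled at the end of infusion and 30 minutes later. SAP 7.11.3 states: "Repeated or unscheduled results will not be included in the summary statistics but will be included in the individual data listings". SAP 7.11.2 keeps repeat and unscheduled laboratory values out of the by-visit summaries but uses them when looking for extremes.

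**Flow rate.** SAP 7.9.4 states: "Infusion flow rate will be calculated as total volume administered ÷ infusion duration". It does not say whether a pause counts toward duration.

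**The concern.** The reaction rate is likely to be the most quoted safety figure from this trial, and safety is a key secondary objective. Whether a patient received a drug meant to prevent the reaction is the first thing needed to read that figure. Use is left to sites, at up to 5 centers, so uptake could be anywhere from none to complete and could differ by center. A reader who sees 20% here against a historical 1 in 3 could not tell whether the cause was premedication, population or chance.

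The vital-sign rule raises a related point. Readings taken because a patient is reacting are unscheduled by nature. They would be visible in a listing but absent from any summarised maximum or minimum.

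**Working it through.** **1. The plan's own figure.** 5/17 = 29.4%, as stated; exact 95% CI 10.3% to 56.0%. That agrees with about 1 in 3. The outcome counts in the same paragraph of Protocol 4.3 do not reconcile: 1 discontinued + 2 halted and restarted + 3 uninterrupted = 6, against 5 reactions.

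**2. The date gap.** Let E be a medication's end date and D the dosing date.
- E > D, or E missing: concomitant.
- E < D: prior.
- E = D: no category.

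A single diphenhydramine dose before the infusion on Day 0 has E = D. It is collected, because the Day 0 pre-dose procedures record all medications since Screening, but the SAP gives it no category. The listings are also of prior and concomitant medications, so its place there is not assured either.

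**3. How far uptake could move the pooled rate.** Pooled rate = (1/3) × [(1 − s) + s × RR], with s the share premedicated and RR the risk ratio with diphenhydramine. The documents give neither s nor RR, and do not say whether the historical 1 in 3 arose with or without premedication. All three inputs are therefore assumptions.

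| RR | s = 0% | 25% | 50% | 75% | 100% |
|---|---|---|---|---|---|
| 1 | 33.3% | 33.3% | 33.3% | 33.3% | 33.3% |
| 0.5 | 33.3% | 29.2% | 25.0% | 20.8% | 16.7% |
| 0.25 | 33.3% | 27.1% | 20.8% | 14.6% | 8.3% |

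With 40 patients, the RR = 0.5 row runs from about 13 reactors to about 7. For comparison, 13/40 = 32.5% has an exact 95% CI of 18.6% to 49.1%.

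**4. What a split can deliver.** Exact 95% CIs: 3/10, 6.7% to 65.2%; 7/20, 15.4% to 59.2%; 10/30, 17.3% to 52.8%. Comparing 1/3 with 1/6 at 20 versus 20 has about 22% power. The split describes; it does not test.

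**5. Timing of vital signs.** For the healthy-volunteer study, Protocol 4.3 states: "All TEAEs presented shortly after infusion start (3-5 min) and resolved on their own shortly thereafter (3-5 min duration)". Reactions were therefore over 3 + 3 = 6 to 5 + 5 = 10 minutes after the start. If an infusion lasts longer than about 10 minutes, the first scheduled post-dose reading comes after such a reaction. This trial's infusion length is blacked out. The only legible length is one to five minutes in ON-1001, where an end-of-infusion reading could fall inside the reaction.

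**6. Flow rate, if pauses were counted.** Understatement for a paused patient = P/(D + P), with running time D and pause P, both assumed. For P = 5 minutes: 5/15 = 33% at D = 10, 5/25 = 20% at D = 20, 5/35 = 14% at D = 30. If 2 of 17 patients pause, the cohort mean falls by 2/17 of that, or 3.9% to 1.7%. Unpaused patients are unaffected.

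**The case against.** The case for leaving the plan alone has real weight. This is a single-arm study of 40 patients with no formal hypothesis test. The overall rate validly estimates risk under the policy actually used, and the SAP plans no comparison with 1 in 3. Events by CTCAE grade, reaction duration, counts of reactors and interruptions, and patient listings are all planned. A non-randomised split gives wide intervals. Clinically relevant vital-sign changes are recorded as adverse events however they are found. All of this stands. It limits the point to reporting, but it does not supply premedication status, and the date gap weakens the listings on which a manual cross-check would rely.

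Three stronger readings are tempting and not supported:
- *That neither the reaction rate nor the flow rate can be interpreted.* The pooled rate has a clear meaning, and a pause could affect flow rate only in paused patients.
- *That flow rate is computed across pauses.* SAP 7.9.4 leaves duration undefined; it does not say elapsed time.
- *That the exposure table would show reactions going with slower infusion.* No table of flow rate by reaction status is planned.

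A reader might also link the one probably related Grade 3 event, high blood pressure, to missed readings. The legible text of Protocol 4.3 does not say it occurred during infusion or was an infusion reaction. Nor does the protocol require readings during a reaction, so the vital-sign point covers only readings that happen to be recorded.

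**Conclusion.** The point holds as a reporting gap in a key secondary objective and does not touch the primary result. Three parts are established from the text alone: no reaction display by premedication although premedication is optional and meant to lower the rate; no category for a medication ending on the dosing date; and different treatment of unscheduled vital signs and unscheduled laboratory values for extremes.

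The size is conditional. The pooled rate could lie anywhere from 8.3% to 33.3% for RR from 0.25 to 1 and uptake from 0 to 100%, taking 1 in 3 as the rate without premedication. If diphenhydramine has no effect, or uptake is uniform and stated, little is lost. The undefined infusion duration is a minor clarification, and its size depends on assumed infusion and pause lengths.

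**What to change.** - **SAP 7.11.1:** report the number of subjects with a reaction, with grade, duration and exact 95% CI, overall and by premedication received (yes/no), labelled descriptive and non-randomised. Show premedication uptake in the SAP 7.9.4 exposure table.
- **SAP 7.9.3:** assign medications ending on the dosing date to a category, so that Day 0 premedication is counted.
- **SAP 7.11.3:** include unscheduled readings, where recorded, in each patient's maximum and minimum from start of infusion to anesthesia, in line with SAP 7.11.2.
- **SAP 7.9.4 (minor):** define infusion duration as time actually infusing, where pause times are captured.
- **Protocol 4.3:** reconcile the outcome counts (6) with the 5 reported reactions.

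The cost is SAP wording, one table split and one added row; SAP 7.1 allows updates before database lock. No change to treatment is involved. Two data checks come first: whether the eCRF separates diphenhydramine given before the infusion from diphenhydramine given to treat a reaction, and whether pause start and stop times are held. The legible text confirms neither. The downside is small subgroups with wide intervals and no causal reading of diphenhydramine.
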